6.4.2.1 Visit 1 (Day 1)

- Verify eligibility criteria
- Patient-reported outcomes, before other interactions with study staff
 - ARCI-M questionnaire (Pre-Dose)
 - Lupus Activity Patient Global Assessment
 - PROMIS-29 Short Form
 - PROMIS Item Bank v2.0 Cognitive Function
 - Fibromyalgia Symptom Scale
- Confirm date of last menstrual period in women of childbearing potential

- Record prior medications
- Vital signs: Height, weight, blood pressure, pulse, respiratory rate, and temperature
- Physical examination
- Physician assessments (all scores will be calculated centrally)
 - o 66/68 joint count
 - SELENA SLEDAI and Flare Index
 - o BILAG 2004
 - Physician's Global Assessment
- AE monitoring
- **Before** study product administration
 - Blood tests
 - Hematology: CBC with differential cell count and platelets
 - Chemistry: Complete metabolic panel, including electrolytes, renal function, and liver function tests
 - CRP
 - Anti-dsDNA antibody titers, C3, and C4 levels
 - o Blood draws for mechanistic studies
 - Whole blood: TruCulture tubes; pro-inflammatory cytokines
 - Plasma: metabolipidomic profile, and JBT-101 plasma concentrations and metabolites; sampled ≥ 2 hours after last solid meal, if possible.
 - RNA: Type 1 IFNα gene signature
 - Serum: future use (if subject provided written consent)
 - PBMC: future use (if subject provided written consent)
- Urine tests before study product administration
 - Urinalysis: microscopic evaluation, and spot protein/creatinine
 - Urine βHCG pregnancy test in women of childbearing potential
- Triplet 12 lead ECGs for medically significant abnormalities and QT/QTc interval prior to study product administration
- Dispense study product according to randomization schedule. Women of child bearing potential must have negative urine βHCG pregnancy test prior to dispensing study product
- Administer study product in clinic and record time of dose

- Observe subject for at least 30 minutes in clinic, until stable in the judgment of the investigator
- 2.5 to 3.5 hours after study product administration
 - ARCI-M questionnaire (Post-Dose)
 - Triplet 12 lead ECGs for QT/QTc interval
 - Blood draws for mechanistic studies
 - Plasma: metabolipidomic profile, and JBT-101 plasma concentrations and metabolites; sampled ≥ 2 hours after last solid meal, if possible
- Reminders:
 - Remind subjects to bring the bottles of study drug with them to their next visit.
 - Remind subject to refrain from taking morning dose before Visit 2. Subjects with visits after 2 PM will be instructed to take their morning dose. This is being done to measure trough plasma concentration of JBT-101 at specified visits.

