- The average half-life ranged from 3.7 to 5.6 hours for single doses.
- There were no effects of the fed state at 20 and 40 mg doses.
- Following JBT-101 administration at 20-40 mg b.i.d. for 7 days in humans, the only observable plasma metabolite of JBT-101 was a glucuronide metabolite [103], which represented 9% of total JBT-101 present in the plasma.

The safety findings in each completed individual clinical trial can be found in detail in the IB for JBT-101. In summary, key safety findings from the two Phase 1 trials (CT-3-01, CPL7075-100-01) and two Phase 2 trials (CPL7075/02/01/001.1, JBT101-SSc-001) are:

- Maximum Tolerated Dose is 180 mg total daily dose
- No deaths and no serious, severe or unexpected AEs related to JBT-101 occurred in any of the studies
- One of 27 (3.7%) JBT-101-treated subjects in the SSc trial (JBT101-SSc-001) withdrew due to a TEAE of moderate dizziness.
- Mild to moderate AEs consistent with CB1/CB2 agonists occurred at higher doses, especially ≥ 150 mg/day total daily dose
- In pooled safety data, TEAEs that occurred in ≥ 5% of 88 JBT-101-treated subjects who received doses within the estimated therapeutic range of ≤ 60 mg total daily dose were dizziness (n = 10, 11%), dry mouth (n = 5, 5.6%), arthralgias (n = 6, 6.8%), GI disturbances (n = 6, 6.8%) and fatigue (n=9, 10.2%). Note that the majority of subjects with GI complaints (6/6), fatigue (8/9) and arthralgias (6/6) were in the SSc trial and all of these symptoms are common in SSc.
- In pooled safety data of all trials (n = 150 total) and all doses of JBT-101, which included 71 subjects who received JBT-101 at doses higher than the estimated therapeutic range, TEAEs that were observed in two or more subjects ≥ 5% of the time included mild dizziness (21.3%), moderate dizziness (10%), mild somnolence (6%), mild nausea (12%), mild dry mouth (8%), and mild fatigue (5.3%) (Table 27 of the Investigator Brochure for JBT-101). These AEs were consistent with CB1/CB2 agonist class effects and showed a dose-response. Most AEs occurred in the highest frequency in subjects who received ≥ 150 mg total daily dose of JBT-101. Adverse events that were reported in ≥ 5% of placebo-treated subjects were headache (5.7%). There were no AEs or laboratory abnormalities that indicated immunosuppression or an increase in rate of infection.

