In support of oral administration q.d. or b.i.d. without regard to fed/fasted state, JBT-101 is well absorbed from the gastrointestinal tract and exhibits dose proportional PK at the doses to be tested in this study. Based on PK results in previous clinical trials, Tmax is expected to be between 2.7 to 3.5 hours for the 5 and 20 mg doses in the current trial, which supports the timing of 3 hours post dosing as an estimate of time of maximal plasma concentrations. The average terminal chemical half-life of JBT-101 in subjects who received 10 mg or 20 mg q.d. in previous studies ranges from 3.7 to 4.4 hours and the biologic effects of JBT-101 are longer, which supports q.d. and b.i.d. testing. Doses to be tested in this study have not shown a significant food effect in a prior clinical study, which supports dosing without regard to fed state.

1.6.3 **Rationale for the Control Arm**

Inclusion of a placebo cohort in this study is important to control for variations in disease activity and AEs that occur commonly in SLE as a result of their disease, co-morbid illness and/or adverse effects of prescribed medications. Because of the relatively short duration of the study and maintenance of the subject's existing medications for musculoskeletal disease activity and pain, the inclusion of a placebo cohort does not impose undue risk on these subjects. To limit risk of increasing disease activity in a placebo-controlled trial, patients with a BILAG A in any organ system at Screening or Visit 1 (Day 1) will be excluded, because those individuals should receive a new treatment for that severely active organ system. Subjects will be maintained on their SLE medications from Screening throughout Visit 6 (Day 113), to reduce a risk of disease flare precipitated by discontinuation of medications to meet entry criteria. Stopping rules will limit the risk of AEs due to severe increases in disease activity.

1.6.4 **Rationale for Mechanistic Studies**

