- Cohort 2 Kit: One bottle of JBT-101 20 mg for a.m. dose and one bottle of placebo for p.m. dose
- Cohort 3 Kit: One bottle of JBT-101 20 mg for a.m. dose and one bottle of JBT-101 20 mg for p.m. dose
- Cohort 4 Kit: One bottle of placebo for a.m. dose and one bottle of placebo for p.m. dose

The bottles will be indistinguishable from each other in appearance, and the kits will be indistinguishable from each other in appearance.

JBT-101 will be dispensed to study subjects in the original packaging with a label clearly indicating that the contents are for investigational purposes only. The label will include conditions for storage, a unique drug ID, and other pertinent information such as Sponsor and caution statement. Neither JBT-101 nor placebo should be used after the expiration date unless a written notification of an expiration date extension is provided by the manufacturer.

If the packaging is damaged, or if there is anything unusual about the appearance or attributes of the pills or bottles, it should not be used. The study drug in question should be quarantined at the study site and the problem immediately reported to DAIT/NIAID or their representative.

5.1.3 **Storage and Handling of Study Product**

DAIT, NIAID will provide the investigational product for the conduct of this protocol and will be responsible for the disposal of unused product.

The investigational product will be stored at the site pharmacy or in the site investigator's locked storage cabinet/safe. Study product will to be stored at room temperature away from temperature and humidity extremes. Storage conditions must be appropriate for small quantities of Controlled Drugs Act Schedule 1 substances. The study product that is returned by the subjects to the site also will be stored under conditions appropriate for small quantities of Controlled Drugs Act Schedule 1, until disposal.

The site pharmacist, site investigator or qualified designee is responsible for investigational product accountability, maintaining accurate logs of study product received, dispensed, returned or destroyed, and ensuring the appropriate amount of study drug is kept on site and that it is used for research purposes only. He/she will perform drug accountability procedures

such as checking drug shipments against the shipping contents form, maintaining a log of the amount of study drug provided to individual subjects, and reconciling used and unused drug supply by subjects and the study unit.

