8.3.4 Plasma Concentrations of JBT-101 and Metabolites

Results of JBT-101 plasma concentrations and metabolites for Visits 1 (Day 1) and Visit 2 (Day 15) will be described, using continuous summary statistics, by visit.

In addition, plasma concentrations will be listed by subject and cohort in a blinded manner, using a mock identification number separate from the subject id, at several times during the trial to determine whether exposure to JBT-101 in the SLE subjects is within the expected

range for the doses administered. Complete analyses of the plasma concentrations and metabolites will be done at the end of the trial.

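### The Visit 2 sample is meant to be a trough, but afternoon visits give a post-dose level, most clearly in the 20 mg once-daily cohort, and the planned summary does not separate the two

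*Protocol*

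**What the plan says.** Section 6.4.2.1 closes with reminders for the next visit. The default is: "Remind subject to refrain from taking morning dose before Visit 2". The next sentence makes the exception: "Subjects with visits after 2 PM will be instructed to take their morning dose". The reason given for the instruction is: "This is being done to measure trough plasma concentration of JBT-101 at specified visits".

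Section 8.3.4 states that Visit 1 and Visit 2 concentrations "will be described, using continuous summary statistics, by visit". The general rules in Section 8.3 add that summaries are tabulated by treatment group. Neither section divides Visit 2 samples by whether the morning dose had been taken, or by time since dose.

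The kit description in Section 5.1.2 gives Cohort 2 as "One bottle of JBT-101 20 mg for a.m. dose and one bottle of placebo for p.m. dose". Cohorts 1 and 3 have active drug in both bottles.

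**The concern.** A trough is the level just before the next active dose. A subject in Cohort 2 who takes the morning capsule and is sampled that afternoon is at mid-interval, some hours past the expected peak and well before the next active dose. The purpose and the instruction therefore conflict for that subject. If the plan is followed as written, the Cohort 2 summary at Visit 2 combines 24 h troughs with post-dose levels, in a proportion set by clinic appointment times.

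Three uses of the data are touched:

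- the Visit 2 description of concentrations, including change from Visit 1 (mechanistic endpoint 6 in Section 3.2.4);
- the reading of the concentration listings made during the trial to check that exposure is in the expected range (Section 8.3.4);
- any exploratory exposure-response work that uses Visit 2 levels (Section 2.3, objective 2).

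**Working it through.** The protocol states no fold difference, so there is no figure of its own to reproduce.

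**Inputs from the protocol**

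- Half-life, single doses (Section 1.3.4): "The average half-life ranged from 3.7 to 5.6 hours for single doses".
- Terminal half-life in subjects who "received 10 mg or 20 mg q.d. in previous studies ranges from 3.7 to 4.4 hours" (Section 1.6.2).
- Time of peak (Section 1.6.2): "Tmax is expected to be between 2.7 to 3.5 hours for the 5 and 20 mg doses in the current trial".
- Cohort 2 takes active drug in the morning only, so a sample with the morning dose held is about 24 h after the last active dose.
- Cohorts 1 and 3 take active drug twice daily.

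**Assumptions not in the protocol**

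- The afternoon draw is 6 to 8 h after the morning dose.
- Doses in the b.i.d. cohorts are 12 h apart. The protocol requires only at least 8 h between doses, so the true gap can differ.

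**Step 1: ratio of afternoon level to trough.** With mono-exponential decline at steady state,

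ratio = 2^((time of trough − time of afternoon draw) / half-life).

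| Half-life (h) | Cohort 2, draw at 8 h: 24 − 8 = 16 h | Cohort 2, draw at 6 h: 24 − 6 = 18 h | b.i.d., draw at 8 h: 12 − 8 = 4 h | b.i.d., draw at 6 h: 12 − 6 = 6 h |
|---|---|---|---|---|
| 3.7 | 20.0 | 29.1 | 2.12 | 3.08 |
| 4.4 | 12.4 | 17.0 | 1.88 | 2.57 |
| 5.6 | 7.2 | 9.3 | 1.64 | 2.10 |

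- Cohort 2 over the full half-life range: 2^(16/5.6) = 7.2 to 2^(18/3.7) = 29.1.
- Cohort 2 with the 3.7 to 4.4 h half-life: 2^(16/4.4) = 12.4 to 2^(18/3.7) = 29.1.
- Cohorts 1 and 3: 2^(4/5.6) = 1.6 to 2^(6/3.7) = 3.1.

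**Step 2: sensitivity.** Widening the draw to 5 to 9 h after the morning dose moves the Cohort 2 range to 2^(15/5.6) = 6.4 to 2^(19/3.7) = 35.1. A one-compartment oral model at steady state, with the absorption rate solved from a peak at 2.7 to 3.5 h and the draw at 6 to 8 h, gives 7.0 to 27.3 for Cohort 2 and 1.6 to 2.9 for the b.i.d. cohorts. The simple formula is adequate.

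**Step 3: effect on the Cohort 2 mean.** If a share f of Cohort 2 is seen after 2 PM and the ratio is R,

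Visit 2 mean / true trough = (1 − f) + f × R.

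| f (assumed) | R = 7.2 | R = 29.1 |
|---|---|---|
| 0 | 1.0 | 1.0 |
| 0.10 | 1.6 | 3.8 |
| 0.25 | 2.5 | 8.0 |
| 0.50 | 4.1 | 15.1 |

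The protocol does not give f, so these rows only illustrate. With no afternoon visits the summary is a clean trough.

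**The case against.** **The large ratio belongs to one arm.** A reader might infer that the whole Visit 2 summary pools levels differing 7- to 29-fold. The documents do not support that. Summaries are by treatment group, so Cohort 2 is not averaged with the b.i.d. cohorts, where the ratio is about 1.6 to 3.1 and a late-afternoon sample falls before the evening active dose and is nearer a trough. All subjects take capsules twice daily to keep the blind, so one instruction has to serve every cohort. This objection stands and limits the size of the point. It does not remove the conflict in Cohort 2.

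**Dose times may already be collected.** Visit 1 requires the dose time to be noted and the Visit 2 list in Section 6.4.2.2 has no matching item, so a reader might infer that the time of the last dose goes unrecorded. That is not shown. Section 7.5.2 names an eCRF page for study drug administration whose fields are not visible.

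**The exposure check does not use a pooled mean.** Section 8.3.4 bases it on listings by subject and cohort. This stands: the by-visit summary does not feed the check. What remains is that an individual Visit 2 value is hard to judge without knowing the time since the last active dose.

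**Exposure-response work need not rely on Visit 2.** There is also a Visit 1 sample 2.5 to 3.5 h after a timed clinic dose, the objective is exploratory, and no model is fixed. This also stands, so the consequence there is conditional.

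**The split is ordinary SAP detail.** In part it is. But the conflict between purpose and instruction is in the protocol's own text, and the summary it describes would report mixed samples at a visit meant for troughs. The listings are also made during the trial, whereas Section 8.10 requires the SAP only before database lock.

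**Conclusion.** The point holds in a limited form. The reminder in Section 6.4.2.1 contradicts its own stated purpose for subjects seen after 2 PM, and Sections 8.3 and 8.3.4 do not keep their samples apart from true troughs.

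In Cohort 2 the afternoon level is about 7 to 29 times the 24 h trough, or about 12 to 29 times with the half-life reported for 10 or 20 mg once daily. In Cohorts 1 and 3 it is about 1.6 to 3.1 times a 12 h trough. These ratios rest on an assumed draw 6 to 8 h after the morning dose and, for the b.i.d. cohorts, on even dose spacing. The effect on any cohort mean is unknown because the share of afternoon visits is not given.

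The consequence is confined to the description of Visit 2 concentrations, the reading of individual values in the exposure listings, and any exploratory exposure-response analysis that uses them. The primary endpoint and the safety event counts are unaffected. The correction is worth making but is not critical to the trial.

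**What to change.** 1. Reconcile the two sentences of the Visit 2 reminder in Section 6.4.2.1 with the trough purpose stated beside them. Which dosing instruction should stand is for the sponsor; the text and the purpose must agree.
2. Confirm that the eCRF captures the clock times of the last morning dose, the last evening dose and the Visit 2 draw, and add whichever is missing.
3. In Section 8.3.4, state that Visit 2 concentrations are summarised by cohort and by pre- or post-dose status.
4. Use actual time since the last active dose when reading the exposure listings and in any exploratory exposure-response analysis. For Cohort 2 that means the last morning dose.

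The cost is one corrected reminder, at most two or three eCRF fields if they are not already there, and a sentence or two in Section 8.3.4. No extra sample, visit or subject is needed.

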6.4.2.2 Visit 2 (Day 15 ± 3 days)

The following procedures will be performed:

- Record concomitant medications
- Vital signs: weight, blood pressure, pulse, respiratory rate, and temperature
- AE monitoring
- Blood tests
 - Hematology: CBC with differential cell count and platelets
 - Chemistry: Complete metabolic panel, including electrolytes, renal function, and liver function tests
- Blood draws for mechanistic studies
 - Plasma: metabolipidomic profile, and JBT-101 plasma concentrations and metabolites; sampled ≥ 2 hours after last solid meal, if possible
 - PBMC: future use (if subject provided written consent)
- Count and record number of capsules the subject has remaining
- Instruct subjects to hold short-acting analgesics for 6 hours and NSAIDs and longacting analgesics for 12 hours prior to the assessments at Visit 3 (Day 29) and remind them to bring the bottles of study drug with them to their next visit.

6.4.2.3 Visit 3 (Day 29 ± 3 days)

- Patient-reported outcomes, before other interactions with study staff
 - ARCI-M questionnaire
 - Lupus Activity Patient Global Assessment
 - PROMIS-29 Short Form
 - PROMIS Item Bank v2.0 Cognitive Function
- Confirm date of last menstrual period in women of childbearing potential
- Record concomitant medications
- Vital signs: weight, blood pressure, pulse, respiratory rate, and temperature
- Physical examination
- Physician assessments (all scores will be calculated centrally)
 - o 66/68 joint count
 - SELENA SLEDAI and Flare Index
 - o BILAG 2004
 - o Physician's Global Assessment
- AE monitoring
- Blood tests
 - Hematology: CBC with differential cell count and platelets
 - Chemistry: Complete metabolic panel, including electrolytes, renal function, and liver function tests
 - o CRP
 - Anti-dsDNA antibody titers, C3, and C4 levels
- Blood draws for mechanistic studies
 - Whole blood: TruCulture tubes; pro-inflammatory cytokines
 - o RNA: Type 1 IFNα gene signature
 - Serum: future use (if subject provided written consent)
- Urine tests
 - Urinalysis: microscopic evaluation, and spot protein/creatinine
 - o Urine βHCG pregnancy test in women of childbearing potential
- Collect returned study product and count and record number of returned capsules
- Dispense study product according to randomization schedule. Women of child bearing potential must have negative urine βHCG pregnancy test prior to dispensing study product.

• Instruct subjects to hold short-acting analgesics for 6 hours and NSAIDs and long-acting analgesics for 12 hours prior to the assessments at Visit 4 (Day 57) and remind them to bring the bottles of study drug with them to their next visit.

6.4.2.4 Visit 4 (Day 57 ± 3 days)

- Patient-reported outcomes, before other interactions with study staff
 - Lupus Activity Patient Global Assessment
 - PROMIS-29 Short Form
 - PROMIS Item Bank v2.0 Cognitive Function
- Confirm date of last menstrual period in women of childbearing potential
- Record concomitant medications
- Vital signs: weight, blood pressure, pulse, respiratory rate, and temperature
- Physical examination
- Physician assessments (all scores will be calculated centrally)
 - o 66/68 joint count
 - SELENA SLEDAI and Flare Index
 - o BILAG 2004
 - Physician's Global Assessment
- AE monitoring
- Blood tests
 - Hematology: CBC with differential cell count and platelets
 - Chemistry: Complete metabolic panel, including electrolytes, renal function, and liver function tests
 - Anti-dsDNA antibody titers, C3, and C4 levels
- Urine tests
 - Urinalysis: microscopic evaluation, and spot protein/creatinine
 - o Urine βHCG pregnancy test in women of childbearing potential
- Collect returned study product and count and record number of returned capsules
- Dispense study product according to randomization schedule. Women of child bearing potential must have negative urine βHCG pregnancy test prior to dispensing study product.

• Instruct subjects to hold short-acting analgesics for 6 hours and NSAIDs and longacting analgesics for 12 prior to the assessments at Visit 5 (Day 85) and remind them to bring the bottles of study drug with them to their next visit.

6.4.2.5 Visit 5 (Day 85 ± 3 days)

- Patient-reported outcomes, before other interactions with study staff
 - ARCI-M questionnaire
 - Lupus Activity Patient Global Assessment
 - PROMIS-29 Short Form
 - PROMIS Item Bank v2.0 Cognitive Function
 - o Fibromyalgia Symptom Scale
 - Treatment Satisfaction Survey
- Confirm date of last menstrual period in women of childbearing potential
- Record concomitant medications
- Vital signs: weight, blood pressure, pulse, respiratory rate, and temperature
- Physical examination
- Physician assessments (all scores will be calculated centrally)
 - o 66/68 joint count
 - SELENA SLEDAI and Flare Index
 - o BILAG 2004
 - Physician's Global Assessment
 - o Treatment Satisfaction Survey
- AE monitoring
- Blood tests
 - Hematology: CBC with differential cell count and platelets
 - Chemistry: Complete metabolic panel, including electrolytes, renal function, and liver function tests
 - o CRP
 - Anti-dsDNA antibody titers, C3, and C4 levels
- Blood draws for mechanistic studies
 - Whole blood: TruCulture tubes; pro-inflammatory cytokines

- o RNA: Type 1 IFNα gene signature
- Serum: future use (if subject provided written consent)
- PBMC: future use (if subject provided written consent)
- Urine tests
 - Urinalysis: microscopic evaluation, and spot protein/creatinine
 - o Urine βHCG pregnancy test in women of childbearing potential
- Triplet 12 lead ECGs for medically significant abnormalities and QT/QTc interval
- Collect returned study product and count and record number of returned capsules. If study product is not returned, subjects should be instructed not to take any additional study drug and arrangements should be made for the subject to return the study product as soon as possible.
- Instruct subjects to hold short-acting analgesics for 6 hours and NSAIDs and longacting analgesics for 12 hours prior to the assessments at Visit 6 (Day 113).

